1.3 Schedule of Activities (SoA)

Table 1-1 Schedule of Activities (SoA)

Procedure	Screening (up to 48 hours before Day 1 ¹)	Intervention Period			Early withdrawal	Efficacy follow-up (Day 14) ² (± 2 days)	EoS efficacy and safety follow-up (Day 28) ² (± 2 days)	Notes
		Day 1 ¹	Daily while hospitalized	Day 10 / hospital discharge				
Informed consent	X							Optional tokenization ICF to be provided for a subset of participants in the United States (see Section 8.4)
Confirmation of COVID-19 infection by nasopharyngeal RT-PCR ³	X							
Inclusion and exclusion criteria	X	X						Recheck clinical status before 1st dose of study intervention
Demographics	X							
Physical examination including height and weight	X			X	X		X ²	Full physical exam and height only at screening

Procedure	Screening (up to 48 hours before Day 1 ¹)	Intervention Period			Early withdrawal	Efficacy follow-up (Day 14) ² (± 2 days)	EoS efficacy and safety follow-up (Day 28) ² (± 2 days)	Notes
		Day 1 ¹	Daily while hospitalized	Day 10 / hospital discharge				
Pregnancy test (urine)	X							All women, including women of childbearing potential and pregnant women, may be enrolled in the study. Pregnancy status should be recorded (see Section 8.3.5). Note: Only females of child bearing potential and pregnant females need to undergo a screening pregnancy test.
Medical history (includes substance usage)	X							History of substance usage or abuse to be recorded but is not exclusionary
Medication history	X							In the prior 3 months
Laboratory assessments (including liver chemistries) ⁴	X ⁴	X ⁴	X (Days 3 and 7 only) ⁴	X ⁴	X ⁴		X ^{2,4}	
12-lead ECG	X							After resting supine for approximately 5 minutes. QRS, QT, QTcF, PR, RR, rate
Vital signs ⁵	X	X	X ⁵	X	X		X	Within 15 minutes prior to study intervention administration

Procedure	Screening (up to 48 hours before Day 1 ¹)	Intervention Period			Early withdrawal	Efficacy follow-up (Day 14) ² (± 2 days)	EoS efficacy and safety follow-up (Day 28) ² (± 2 days)	Notes
		Day 1 ¹	Daily while hospitalized	Day 10 / hospital discharge				
Randomization		X						

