Study intervention, TID ⁶		X	X	X				A staggered dosing approach will be used for the first 10 participants (up to the first IDMC safety review). Each RESP301 dose will be administered by intermittent inhalation to monitor the tolerability and response to RESP301 (see Sections 6.1 and 9.6). Where possible study intervention should be administered at approximately the same times each day At least 6 hours between 2 consecutive doses
AE/SAE review	X	X	X	X	X	X	X	
Concomitant medication review	X	X	X	X	X	X	X	
Pre Treatment oxygen / respiratory assessment ⁷	X	X	X	X				
SpO ₂ on room air (after at least 1 minute) prior to study intervention administration and immediately at the end of nebulization ⁶		X	X	X				See Section 8.1.2

Procedure	Screening (up to 48 hours before Day 1 ¹)	Intervention Period			Early withdrawal	Efficacy follow-up (Day 14) ² (± 2 days)	EoS efficacy and safety follow-up (Day 28) ² (± 2 days)	Notes
		Day 1 ¹	Daily while hospitalized	Day 10 / hospital discharge				
Modified WHO ordinal scale	X	X	X	X		X	X	See Section 8.1.1
NEWS 2 assessment ⁷		X	X	X				Prior to study intervention in the morning. See Section 8.1.3

Abbreviations: AE=adverse event; aPTT= activated partial thromboplastin time; CBC=complete blood count; Chem 7=blood chemistry panel (sodium, potassium, chloride, bicarbonate/CO₂, blood urea nitrogen, creatinine, glucose); CV=cardiovascular; ECG=electrocardiogram; IDMC=Independent Data Monitoring Committee; LFTs=liver function tests; mHb=methemoglobin; PT/INR=prothrombin time/international normalized ratio; RT-PCR=reverse transcription-polymerase chain reaction; SAE=serious adverse event; TID=three times daily.

1. Screening and randomization may be on the same day, providing all eligibility criteria are met.
2. For participants who are already discharged at either the Day 14 or Day 28 (EoS) follow-up, there will be a phone call to check AEs/SAEs, concomitant medications, and modified WHO ordinal scale. At EoS, safety laboratory tests (nitrite and mHb only) and weight will be collected for participants in hospital only.
3. COVID-19 infection must be confirmed and documented in chart with a positive result on a validated test.
4. At Screening: CBC, chem 7, mHb, LFTs, and coagulation (PT/INR, aPTT).
On Day 1, Day 3, Day 7 and Day 10, or early withdrawal: CBC, chem 7 (per SOC), and mHb.
On Day 28: nitrite and mHb (participants in hospital at EoS only).

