7.1 Permanent Discontinuation of Study Intervention

It may be necessary for a participant to permanently discontinue (definitive discontinuation) study intervention. If study intervention is definitively discontinued, the participant will remain in the study to be evaluated for the Day 14 and Day 28 safety follow-ups. See the SoA (Table 1-1) for data to be collected at the time of discontinuation of study intervention and follow-up and for any further evaluations that need to be completed.

Study intervention will be permanently discontinued prior to 10 days if the participant:

- Improves to level 1 or 2 of the modified WHO ordinal scale;
- Progresses to a level > 4 of the modified WHO ordinal scale.

Additionally, study intervention should be permanently discontinued in the following circumstances:

1. Discontinuation of study intervention for abnormal liver tests should be considered if the Investigator believes that it is in best interest of the participant. The development of alanine aminotransferase (ALT) $\geq 3 \times$ ULN and bilirubin $\geq 2 \times$ ULN or ALT $\geq 3 \times$ ULN and international normalized ratio (INR) > 1.5 , if INR is measured, which may indicate severe liver injury (according to Hy's Law), must be reported as an SAE and the study intervention discontinued.
2. If, as part of normal clinical follow-up, a clinically significant change in ECG is identified, the Investigators should exercise their clinical judgement to decide whether continuing study intervention administration is in the best interest of safety of the participant.
3. AE/SAE if the Investigator believes that it is in best interest of the participant, including the following:
 - Development of significant bronchospasm * or worsening of cough that is not tolerated by the participant and leads to immediate discontinuation of the nebulization.
 - Progressive COVID-19 requiring initiation of invasive ventilation or high flow oxygen.
 - Development of mHb level above 3%.

- Inability to safely continue receiving study intervention due to compromised respiratory status while off supplemental oxygen and receiving nebulized therapy (manifest by drop in SpO₂, increased respiratory rate or clinical other findings).

Refer to the SoA (Table 1-1) for data to be collected at the time of study intervention discontinuation and follow-up and for any further evaluations that need to be completed.

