8.2.4 Clinical Safety Laboratory Assessments

Refer to Appendix 3 for the list of clinical laboratory tests to be performed and to the SoA (Table 1-1) for the timing and frequency.

The Investigator must review the laboratory report, document this review, and record any clinically relevant changes occurring during the study in the AE section of the CRF. The laboratory reports must be filed with the source documents. Clinically relevant abnormal laboratory findings are those which are not associated with the underlying disease, unless judged by the Investigator to be more severe than expected for the participant's condition.

All laboratory tests with values considered clinically abnormal during participation in the study or within 4 days after the last dose of study intervention should be repeated until the values return to normal or baseline or are no longer considered clinically significant by the Investigator or Medical Monitor.

- If such values do not return to normal/baseline within a period of time judged reasonable by the Investigator, the etiology should be identified, where possible, and the Sponsor notified.

- All protocol-required laboratory assessments, as defined in Appendix 3, must be conducted in accordance with the Laboratory Manual and the SoA (Table 1-1).
- If laboratory values from laboratory assessments not specified in the protocol and performed at the institution's local laboratory result in the need for a change in participant management or are considered clinically relevant by the Investigator (e.g., are considered to be an SAE or an AE), then the results must be recorded in the CRF.

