10.3 Appendix 3: Clinical Laboratory Tests

The tests detailed in Table 1-1 will be performed by the local laboratory.

Protocol-specific requirements for inclusion or exclusion of participants are detailed in Section 5 of the protocol. Additional tests may be performed at any time during the study as determined necessary by the Investigator or required by local regulations.

Table 10-1 **Protocol-Required Laboratory Assessments**

Laboratory Assessments	Parameters									
Hematology	
CBC without differential:
 
White blood cell (WBC) count, red blood cell (RBC) count, hemoglobin, hematocrit, mean corpuscular volume, mean corpuscular hemoglobin, mean corpuscular hemoglobin concentration, red cell distribution width, platelet, mean platelet volume
 
Methemoglobin, nitrite
									
Clinical Chemistry ¹	Blood urea nitrogen Creatinine Glucose non-fasting	Potassium Sodium Chloride	Aspartate Aminotransferase Alanine Aminotransferase/ Alkaline phosphatase Lactate dehydrogenase		Total bilirubin Coagulation (PT/INR, aPTT)					
Other Screening Tests	
Highly sensitive urine human chorionic gonadotropin pregnancy test (for women of childbearing potential and pregnant women)²
 
The results of each test must be entered into the eCRF.
									
NOTES:										

1 Details of liver chemistry stopping criteria and required actions and follow-up assessments after liver stopping or monitoring event are given in Section 7.1. All events of ALT $\geq 3 \times$ ULN and bilirubin $\geq 2 \times$ ULN or ALT $\geq 3 \times$ ULN and international normalized ratio (INR) > 1.5, if
										

Laboratory Assessments	Parameters
	INR is measured, which may indicate severe liver injury (possible Hy's Law), must be reported as an SAE and the study intervention discontinued.
	2 Local urine testing will be standard for the protocol unless serum testing is required by local regulation or IRB/IEC.

Investigators must document their review of each laboratory safety report.

10.4 Appendix 4: Adverse Events: Definitions and Procedures for Recording, Evaluating, Follow-up, and Reporting

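### No liver test is scheduled after screening to serve the mandatory liver stopping rule, and exclusion criterion 5 omits two groups that Table 2-1 says it excludes

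*Protocol*

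**What the plan says.** **Liver rule.** Most of the liver text in Section 7.1 is left to the investigator's judgement, but one part is not. ALT at or above 3 × ULN with bilirubin at or above 2 × ULN, or the same ALT with INR above 1.5, "must be reported as an SAE and the study intervention discontinued". Only INR is made conditional on having been measured. Appendix 3, Table 10-1, note 1 repeats the rule and refers back: "Details of liver chemistry stopping criteria and required actions and follow-up assessments after liver stopping or monitoring event are given in Section 7.1".

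**Liver tests.** Section 8.2.4 leaves the timing of laboratory tests to the Schedule of Activities (SoA, Table 1-1). The row label there begins "Laboratory assessments (including liver chemistries", and the row is ticked at screening and at later visits. Footnote 4, attached to the label and to each ticked cell, sets the content. It first gives "At Screening: CBC, chem 7, mHb, LFTs, and coagulation (PT/INR, aPTT", and then, for the treatment period, "On Day 1, Day 3, Day 7 and Day 10, or early withdrawal: CBC, chem 7 (per SOC), and mHb". The abbreviation list has "Chem 7=blood chemistry panel (sodium, potassium, chloride", continuing with bicarbonate, urea nitrogen, creatinine and glucose. For Day 28, footnote 2 says "At EoS, safety laboratory tests (nitrite and mHb only) and weight will be collected for participants in hospital only".

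**Entry limits.** Exclusion criterion 13 removes patients with ALT or AST above 5 × ULN. It sets no bilirubin limit.

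**Bronchospasm.** Table 2-1 (Section 2.2.1) names exclusion criterion 5 as the means of keeping out two groups: patients known to have moderate or severe hyperreactive airways, and patients with significant bronchospasm on examination. Criterion 5 in Section 5.3 lists uncontrolled asthma and past severe bronchospasm, and nothing else.

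**The concern.** A mandatory stopping rule needs data to act on. Here the protocol requires action on an ALT and bilirubin combination but schedules neither analyte once dosing begins. Whether the rule operates then depends on what each hospital orders for its own reasons. In an open-label trial that can differ between sites and between arms.

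The second mismatch is of the same kind. The benefit-risk conclusion in Section 2.2.3 rests on the measures taken to reduce risk, and Table 2-1 counts an exclusion among them. Sites enrol from Section 5.3, not from Table 2-1. If the exclusion is not written in Section 5.3, that mitigation does not operate as described. Section 7.1 itself states that inhaled citric acid and mannitol can provoke bronchospasm in patients with hyperresponsive airways.

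**Working it through.** The plan gives no figure to reproduce. The check sets the provisions side by side and counts.

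**Part 1: can scheduled data trigger the liver rule?**

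| Time point (SoA row) | Tests under footnote 4 | ALT, AST or bilirubin |
|---|---|---|
| Screening | CBC, chem 7, mHb, LFTs, coagulation | Yes |
| Day 1 | CBC, chem 7, mHb | No |
| Day 3 | CBC, chem 7, mHb | No |
| Day 7 | CBC, chem 7, mHb | No |
| Day 10 / discharge | CBC, chem 7, mHb | No |
| Early withdrawal | CBC, chem 7, mHb | No |
| Day 28 (in hospital only) | Nitrite, mHb | No |

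- Chem 7 has 7 components, of which 0 are liver analytes.
- Time points after screening with a liver analyte: 0 of 6.
- Days 3 and 7 are the laboratory days that can clearly inform a decision to stop: 0 of 2. Day 10 is the last dosing day.
- Exposure: 3 doses a day × 10 days = up to 30 doses.
- Longest gap from the only scheduled liver test to the last dosing day: 2 days (the 48-hour screening window) + 9 days (Day 1 to Day 10) = 11 days.
- ALT values that are eligible under criterion 13 and already meet the ALT half of the rule: 3 to 5 × ULN.

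The repeat rule in Section 8.2.4 ("All laboratory tests with values considered clinically abnormal during participation in the study or within 4 days after the last dose of study intervention" are to be repeated until normal, back to baseline, or no longer clinically significant) helps only in part. A raised screening ALT may be repeated, but that value is itself the baseline. A normal screening bilirubin gives no reason to repeat it. A participant whose screening values were all normal has no scheduled test that could reveal the combination.

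**Was reliance on routine care intended?** The wording suggests not. The ECG item in the same list in Section 7.1 is expressly tied to ordinary clinical follow-up; the liver item is not. The history of Amendment 2.0, used here only as evidence of intent, says that mHb was added to footnote 4 so that it could be checked against the discontinuation criteria. The same amendment put the Hy's Law wording into Section 7.1, with no matching liver test in footnote 4.

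**Part 2: who is excluded?**

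| Patient | Table 2-1 says excluded | Criterion 5 excludes |
|---|---|---|
| Known moderate hyperreactivity, asthma controlled, no severe episode | Yes | No |
| Significant bronchospasm on examination, no uncontrolled asthma, no severe history | Yes | No |
| Mild asthma, not controlled | No | Yes |

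No other criterion names the first two groups. Criterion 6 concerns chronic respiratory disease needing more than 12 hours of oxygen a day before admission. Criterion 2 is a judgement about tolerating roughly 8 minutes of nebulization. Section 6.3 counts treated chronic lung disease among the stratification risk factors, so such patients are expected in the trial.

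**The case against.** **Liver.** The strongest reply is that the rule still works without scheduled surveillance. Participants enter as inpatients under institutional care, Appendix 3 allows additional tests at any time, and Section 8.2.4 requires clinically relevant results from non-protocol tests to be recorded. Section 4.2 explains that procedures were kept minimal on purpose. Table 2-1 lists no hepatic risk for RESP301, and an ALT of 3 to 5 × ULN is only half of the trigger. All of this stands, and it limits the weight of the point. It does not answer it: the protocol makes the action mandatory without ensuring the data, and the liver item lacks the routine-care wording that the ECG item has.

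A reader might infer that the rule is inoperative, or that the row label and footnote 4 give sites two competing instructions. The documents support neither. Unscheduled tests can trigger the rule, and footnote 4 hangs on the label and on every ticked cell, so it settles what is done. The label is loose wording.

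**Criterion 5.** A reader might also infer that criterion 5 is simply a weaker form of Table 2-1. It is not, because mild uncontrolled asthma falls under criterion 5 alone. It can fairly be said that Section 5.3 is the operative list, that the documents do not show which wording was meant, and that correcting Table 2-1 would also restore agreement. Safeguards overlap: criterion 2, the clinical recheck before the first dose, SpO₂ and heart-rate alarms, supervised first dosing, discontinuation for bronchospasm, and staggered dosing until the first IDMC review is complete. Section 7.1 places the study concentrations below provocative levels. A patient with evident bronchospasm would probably be stopped by criterion 2; controlled moderate hyperreactivity is the clearer gap. These safeguards reduce the consequence but do not make the Table 2-1 statement true.

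**Conclusion.** Both mismatches stand in the current text and should be corrected. They are separate and should be judged separately.

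1. After screening, 0 of 6 laboratory time points include a liver analyte, over up to 30 doses and up to 11 days from the last scheduled liver test. The mandatory rule can fire on treatment only through routine-care, discretionary or repeat testing. This assumes that footnote 4 governs the content of each visit, which is how the table is built.
2. Criterion 5 leaves out two groups that Table 2-1 says it excludes. The documents give no frequency for either group, so the number affected cannot be stated. Nor can the number protected by staggered dosing: 10 treated participants is a floor, because the review follows completion of the study by 10 participants and no accrual rate is given.

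Nothing in the protocol points to a known hepatic signal, and neither matter touches the primary analysis, the sample size or the type I error. The case for change rests on safety and consistency at low cost.

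**What to change.** **Liver.** Add ALT, AST and total bilirubin to footnote 4 on Days 3 and 7, where they can inform stopping, and on Day 10 or early withdrawal, where they mainly serve SAE detection. Leave INR conditional on being measured. Relabel the SoA row so that liver chemistries apply only at the visits footnote 4 lists; this also removes any suggestion of liver tests on Day 1 and Day 28.

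Cost: 3 analytes × 3 visits = up to 9 extra local assays per participant. Table 10-1 already lists the analytes. CBC and mHb already require a draw on those days, and Section 8 allows about 20 mL per occasion on Days 3, 7 and 10. A chemistry tube may be additional where chem 7 is not part of local care. Giving the liver item the same routine-care wording as the ECG item would be cheaper and would make the text consistent, but it would leave the data gap open.

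**Criterion 5.** Keep the present wording and add the two missing groups: a known history of moderate or severe bronchial hyperreactivity, and signs of significant bronchospasm on examination. The complete screening examination (Section 8.2.1) already covers the respiratory system, so no new procedure is needed. The cost is slightly narrower eligibility, by an amount the documents do not allow one to estimate, and it may fall on patients with chronic lung disease. If the sponsor did not intend these exclusions, correct Table 2-1 instead, so that the benefit-risk assessment does not rely on them.

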5. Vital signs: temperature, heart rate, blood pressure, respiratory rate. Vital signs to be repeated as per SOC during treatment period.
6. Study intervention comprises the following procedures which are to be done in order and as quickly as possible:
 - a. Discontinuation of supplemental oxygen administration where applicable *
 - b. Close participant oversight by trained health care professional until SpO₂ is stable on ambient air after one minute at least *
 - c. Recording of SpO₂ * pre-nebulization on ambient air
 - d. Preparation of the admixture of RESP301 (to be done no longer than 5 minutes before administration)*
 - e. Administration of the nebulization via a vibrating mesh nebulizer while monitoring SpO₂ and heart rate (alarms set to 89% and 120 beats / min, or as indicated by the Investigator, for stopping study intervention administration and resuming supplemental oxygen where applicable) * If the participant is unable to tolerate nebulization without supplemental oxygen, nasal oxygen may be administered during nebulization.
 - f. Discontinuation of nebulization 20 minutes after preparation of admixture, or no product left in the device, whichever comes first *
 - g. Recording of SpO₂ * post nebulization on ambient air
 - h. Resuming supplemental oxygen where applicable*
 - i. Participant oversight until SpO₂ is stable *
 - j. Recording of SpO₂ *

* for participants on active treatment arm only
7. Participant remains on supplemental oxygen if applicable, and measurements made of respiratory rate, heart rate and SpO₂ and a record of oxygen flow level including mode (nasal cannula, mask)

2 Introduction

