5.2 Inclusion Criteria

Participants are eligible to be included in the study only if all of the following criteria apply:

Age

1. Participant is ≥ 18 years of age, at the time of signing the informed consent.

Type of Participant and Disease Characteristics

2. Participant has laboratory-confirmed SARS-CoV-2 infection as determined by reverse transcriptase polymerase chain reaction (RT-PCR) or other approved clinical testing prior to randomization.
3. Participant is hospitalized in relation to COVID-19 (WHO level 3 & 4).

Sex

4. Participant is male or female. All females of childbearing potential, including pregnant females, must consent to urine pregnancy testing at screening to be eligible for the study. (Females who are not of childbearing potential do not need to undergo a pregnancy test at screening).

Informed Consent

5. Participant is capable of giving signed informed consent as described in Appendix 1 which includes compliance with the requirements and restrictions listed in the informed consent form (ICF) and in this protocol.

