8.1 Efficacy Assessments

8.1.1 Modified WHO Ordinal Scale

A modified WHO ordinal scale will be used for consistency with the recent study of lopinavir-ritonavir in adults hospitalized with severe COVID-19 (Cao et al, 2020), to record the participant's status at the time of assessment. The modified WHO ordinal scale includes the following levels:

1. Not hospitalized, no limitations on activities;
2. Not hospitalized, limitation on activities;
3. Hospitalized, not requiring supplemental oxygen;

4. Hospitalized, requiring supplemental oxygen;
5. Hospitalized, on non-invasive ventilation or high-flow oxygen devices;
6. Hospitalized, on invasive mechanical ventilation or extra corporeal membrane oxygenation (ECMO);
7. Death.

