9.1 Statistical Hypothesis

RESP301 reduces the rate of progression in the modified WHO ordinal scale in COVID-19 (see Section 8.1.1).

The endpoint of worsening level on the WHO ordinal scale represents a composite endpoint of scales above the entry level, being (i) death (level 7), (ii) hospitalized, on invasive mechanical ventilation or ECMO (level 6), (iii) hospitalized, on non-invasive ventilation or high-flow oxygen devices (level 5) , or, for those patients who were recruited at WHO ordinal scale 3, (iv) hospitalized, requiring supplemental oxygen.

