9.2 Sample Size Determination

A total of 300 hospitalized participants with confirmed COVID-19 will be randomized 2:1 to receive RESP301+SOC (200 participants) or SOC alone (100 participants).

The comparison between the treatment arms for the primary endpoint will have approximately 80% power and alpha level 0.025 (one-sided) to demonstrate significant reductions (15% versus 30%) of the primary endpoint between RESP001+SOC and the Control arm (SOC), a 50% relative reduction for the proportion of participants who progress by at least one level on the WHO ordinal scale (see definition of the primary endpoint).

Two interim analyses are planned (see Section 9.5 for details):

1. The first IDMC interim analysis will take place after the first 60 participants have completed Day 10 of the study to evaluate whether the study can be stopped for futility based on change from baseline in room air SpO₂. For a final decision to stop the study for futility the results on other endpoints will be considered as well.
2. The second interim analysis will take place after 150 participants have completed Day 14 post-randomization based on event rate for the primary endpoint. The purpose of the second interim analysis will be futility as well as a potential sample size re-estimation in case the actual results differ from the original assumptions.

In addition to the review of efficacy data, safety will be assessed at each of the interim analysis by the IDMC. Further details are provided in Appendix 5.

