9.4.2 Primary Endpoint

The primary endpoint is the proportion of participants who progress by at least one level higher on the modified WHO ordinal scale by Day 14.

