9.5 Interim Analyses

Two interim analyses will be performed.

1. The first analysis will be conducted when about 60 participants (40 participants in the RESP301+SOC arm and 20 participants in the SOC arm) have completed the Day 10 assessment. The purpose of this analysis is to evaluate efficacy of RESP301 with the application of a futility criterion based on the results on SpO₂ change from baseline on Day 10. The following futility criterion will be used for this first interim analysis:

If the difference in the percentage of participants with at least a 2% improvement in SpO₂ between both treatment arms is less than 5%, benefit of RESP301 treatment is not expected. For a final decision to stop the study for futility the results on other endpoints will be considered as well.

As no other modification of the study at the time of the first interim analysis is considered, no adjustment of the alpha level is required.

2. The second interim analysis will be conducted after 150 participants (100 participants in the RESP301+SOC arm and 50 participants in the SOC arm) have completed the Day 14 assessment. The purpose of this analysis is the assessment of futility or a sample size re-estimation in case the actual results differ from the original assumptions for the power calculations of the study, related to the percentage of participants meeting the primary endpoint in the control arm and/or the relative treatment benefit achieved in the RESP301+SOC arm compared to the SOC arm.

To account for the multiple testing due to the second interim analysis an adjustment for the type I error alpha will be applied using the Haybittle-Peto approach which would spend one sided alpha=0.0005 at the second interim analysis and leave one-sided nominal alpha of 0.0249 for the final analysis. The futility criterion for the second interim analysis will be based on the conditional power (CP) for the final results based on the assumption that the remainder of the study will follow the same trend as observed in the interim analysis. If CP at the time of the second interim analysis is less than 20% consideration will be given to stop the study for futility. At the same time sample size re-estimation will be performed to achieve 80% power at the end of the study. The methodology for the adjustment and the procedure to maintain the type I error level will be described in greater detail in the SAP.

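### Nasal oxygen given only for a RESP301 nebulization can be scored as WHO level 4, a primary event for level-3 entrants by a route that exists only in the active arm

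*Protocol*

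**What the plan says.** All references are to the amended protocol (WHO grades 3 and 4).

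- Section 5.2 admits patients at level 3 or level 4. Section 8.1.1 defines level 4 as "Hospitalized, requiring supplemental oxygen", with no minimum duration and no remark on oxygen given for a procedure. The scale records status when the assessment is made.
- Section 9.4.2 gives the primary endpoint as the "proportion of participants who progress by at least one level higher on the modified WHO ordinal scale by Day 14". Section 9.1 lists the components of this composite, including, "for those patients who were recruited at WHO ordinal scale 3, (iv) hospitalized, requiring supplemental oxygen".
- Section 1.3, footnote 6e, states: "If the participant is unable to tolerate nebulization without supplemental oxygen, nasal oxygen may be administered during nebulization". Table 6-1 repeats it. Neither place limits it to participants who entered on oxygen.
- Footnote 6 marks the nebulization steps as active-arm only. Section 4.1 gives controls standard of care alone, with no placebo nebulization.
- The Schedule of Activities has the WHO level scored daily in hospital, without a time of day. NEWS 2 is fixed before the morning dose, and the oxygen and respiratory assessment is labelled pre-treatment.

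**The concern.** While only level-4 patients were eligible, oxygen during dosing could not change a participant's level. Once level-3 patients were admitted, level 4 became an outcome for them. The current endpoint also lacks the qualifier in the superseded text that tied progression to COVID-19, so nothing in the definition sets procedural oxygen aside.

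The criterion for giving this oxygen, inability to tolerate dosing without it, is close in wording to the definition of level 4. An unblinded assessor who scores during or soon after a nebulization could reasonably record level 4. One such score is enough, because the endpoint asks for no confirmation. Another site could score the same participant, on room air between doses, as level 3.

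At stake are events added in one arm only, site-dependent scoring of the primary endpoint in level-3 entrants, and the same effect on time to progression, a key secondary endpoint in 9.4.3.

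**Working it through.** **Inputs from the protocol.** Rates of 30% (control) and 15% (active), 100 and 200 participants, one-sided alpha 0.025 and about 80% power (9.2). Section 9.5 says the second interim will "leave one-sided nominal alpha of 0.0249 for the final analysis"; using 0.0249 changes the powers below by no more than about 0.1 percentage point.

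**Reproducing the design figure.** For the uncorrected pooled test of two proportions:

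- Pooled rate = (30 + 30)/300 = 0.20. Null SE = √(0.20 × 0.80 × (1/100 + 1/200)) = 0.0490.
- Alternative SE = √(0.30 × 0.70/100 + 0.15 × 0.85/200) = 0.0523.
- Power = Φ((0.15 − 1.96 × 0.0490)/0.0523) = Φ(1.03) = 84.9%.

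This test needs N = 264 for 80%. With a continuity correction N = 291, and exact power at 100 and 200 is 81.6% (81.4% for Fisher's test). The stated 300 for about 80% therefore reproduces with a corrected or Fisher calculation. The figures below use the uncorrected formula.

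**Effect of scoring procedural oxygen as level 4.** Let f be the share entering at level 3, and q the share of otherwise event-free level-3 active participants scored level 4 only because of oxygen during a nebulization. The documents give neither, so both are assumptions. The control rate is held at 30%, and the 15% is taken to apply equally at levels 3 and 4.

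Active rate = 0.15 + f × 0.85 × q; extra events = 200 × f × 0.85 × q.

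| f | q | Extra active events | Active rate | Relative risk | Power |
|---|---|---|---|---|---|
| any | 0 | 0 | 15.0% | 0.50 | 84.9% |
| 50% | 2% | 1.7 | 15.9% | 0.53 | 80.1% |
| 50% | 5% | 4.25 | 17.1% | 0.57 | 71.6% |
| 50% | 10% | 8.5 | 19.3% | 0.64 | 55.0% |
| 25% | 5% | 2.1 | 16.1% | 0.54 | 78.8% |
| 75% | 5% | 6.4 | 18.2% | 0.61 | 63.6% |

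These are fixed-sample, unstratified figures. They ignore the interim analyses and the stratified test.

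**Second interim.** Among 100 active participants, f = 50% and q = 10% adds 100 × 0.5 × 0.85 × 0.10 = 4.25 events. The table in 10.5.3, with 15 of 50 control events, gives conditional power of 90% for 15 active events and 55% for 19, where the total needed becomes 483. A few such scores could change the adaptation.

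**How far timing could shrink q.** Exclusion criterion 2 puts a nebulization at about 8 minutes, and 6.2.1 limits it to 20. If the daily assessment fell at a random moment (an assumption), it would coincide with one oxygen-assisted dose with probability 8/1440 = 0.6% to 20/1440 = 1.4%. If 5% of these participants needed oxygen at one dose, q would be at most 0.05 × 0.014 = 0.0007, and the active rate 0.15 + 0.5 × 0.85 × 0.0007 = 15.03%. If a site instead recorded the highest support used that day, q would equal the whole share given oxygen. The unspecified scoring time therefore decides whether the effect is negligible or material.

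**The case against.** The strongest reply is that the protocol never says procedural oxygen makes a participant level 4. The scale records status at the assessment, and a patient on room air between doses is naturally level 3. Oxygen flow and mode are already recorded before treatment (footnote 7), so the routine daily oxygen record is pre-dose. This stands against any claim that the event is certain. It does not close the gap, because nothing ties the WHO score to that pre-treatment record.

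A reader might also treat the stop at SpO₂ 89% as a second route to an event. The text does not support that: oxygen is resumed only where applicable, and a level-3 participant has none to resume.

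Frequency is limited by exclusion criteria 1, 2 and 5 and by the rule in 7.1 on respiratory compromise during nebulization. The bias is conservative: it does not raise the false-positive risk in favour of RESP301, and sample size re-estimation could recover some power at the cost of more participants. All of this stands.

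Desaturation caused by the nebulized drug may also be a real harm, so setting it aside is a choice of estimand. An exemption judged by unblinded staff, in one arm and without a time limit, could hide true worsening. That is a good reason for a narrow, time-bound exemption that keeps the events visible.

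Finally, scoring conventions often sit in the SAP or CRF guidance, which are not shown. But the time of assessment belongs to the Schedule of Activities. Section 8.1.2 documents oxygen in use at each oximetry reading, but it does not ask whether that oxygen was for dosing only, so later analysis may be unable to separate the two.

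**Conclusion.** The point holds as an unguarded scoring rule. The current text permits, but does not compel, a primary event in level-3 entrants by a route found only in the open-label active arm. Controls can still reach level 4 through disease; the asymmetry concerns this route alone.

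The bias runs against RESP301, dilutes the relative risk and lowers power. Its size is unknown. With half entering at level 3 and q between 2% and 10%, the active rate would be 15.9% to 19.3% and fixed-sample power about 80% to 55% instead of 85%. A reader might take these powers as forecasts. They are not: f and q are both assumed, and q counts only participants actually scored level 4. Scoring between doses would make the effect much smaller. This is a cheap and worthwhile improvement, not a flaw that invalidates the design.

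**What to change.** - **Schedule of Activities and 8.1.1:** score the daily WHO level before the first dose of the day, together with the pre-treatment oxygen assessment and NEWS 2, and at the same morning time in controls. This alone removes most of the asymmetry.
- **9.4.2:** state that oxygen used only during a nebulization does not by itself count as level 4, and that oxygen still in use at the next scheduled assessment does. This sets a fixed end to the exemption.
- **CRF:** add a flag for dosing-only oxygen and keep reporting it as a tolerability event.
- **Analysis:** add a sensitivity analysis of the primary endpoint that counts dosing-only oxygen as progression.

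The cost is one extra CRF flag, a fixed scoring time and a few sentences of protocol text. The clinical rules for giving oxygen do not change.
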